5.1.2.6 Progression-free Survival per RECIST v1.1 (PFS)

PFS is defined as the time from the start of the study treatment until death from any cause or radiographic disease progression assessed per RECIST v1.1 by investigator assessment, whichever occurs first.

Table 3 PFS Definition

PFS		
Situation	Date of Event or Censor	Outcome
No evaluable post-baseline imaging assessments, no death	Date of first dose (Day 1)	Censor
Participant did not receive new anti-cancer therapy:		
Radiographical progression documented per RECIST v1.1	Date of radiological disease progression	Event

PFS		
Situation	Date of Event or Censor	Outcome
No radiographical progression, but death recorded on eCRF	Date of death	Event
Neither radiographical progression nor death	Date of last disease assessment	Censor
Participant received new anti-cancer (ACT) therapy:		
Radiographical progression documented per RECIST v1.1 after new ACT	Date of last radiological assessment before start of new anti-cancer therapy	Censor
Radiographical progression documented per RECIST v1.1 before new ACT	Date of radiological disease progression	Event
No radiographical progression before new ACT but death recorded	Date of last radiological assessment before start of new anti-cancer therapy	Censor
No radiographical disease progression nor death	Date of last radiological assessment before start of new anti-cancer therapy	Censor
Missed >=2 scheduled radiological assessments		
If radiographical progression or death occurs after missing 2 scheduled radiological assessments	Date of last radiological assessment before missing 2 scans	Censor

PFS = Date of Event or Censor – Date of First Dose +1

Missing 2 scheduled imaging assessments:

Missing 2 scheduled imaging assessments is defined as the gap between two imaging assessments being more than 140 days (2.5 times the scheduled imaging assessment interval (2.5 x 56 days)). Imaging assessments after first iUPD will be excluded in PFS derivation.

Note: Participant cannot be censored at “NE”. If NE is the only previous assessment, then PFS will be censored at Day 1.

To apply the cut-off date to PFS is to exclude those tumor assessments after cut-off date and anti-cancer therapy date after cut-off date in the analysis.

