1.3 Schedules of Assessments

Table 1 Schedule of Assessments – Dose Escalation Cohort

Visit Days	Scr	Treatment ^a															EOT ^t
		Cycle 1					Cycle 2					Cycles 3–4 ^b			Cycles 5–6 ^c		
-28 to -1	1	2	4	8	15	1	2	4	8	15	1	8	15	1	8	15	
Window(days)		0	0	0	±1	±1	±1	0	±1	±1	±3	±1	±1	±3	±1	±1	+7
Signed ICF	X																
Medical and Disease History	X																
Physical Examination ^d	X ^d	X ^d	X	X	X	X	X ^d	X	X	X	X ^d	X	X	X ^d	X	X	X ^d
Vital Signs	X	X ^e	X	X	X	X	X ^e	X	X	X	X ^e	X	X	X ^e	X	X	X
ECOG Performance	X	X ^f	X	X	X	X	X ^f		X	X	X ^f	X	X	X ^f	X	X	X
Chest X-ray	X ^g																
12-Lead ECG ^h	X	X ^h				X	X ^h			X	X ^h				X ^h		X
Prior and Concomitant Medications	X ⁱ	X	X	X	X	X	X	X	X	X	X	X	X	X	X	X	X
Pregnancy Test for WOCBP	X ^j	X ^j					X ^j				X ^j			X ^j			X ^j
Clinical Laboratory Tests (chemistry, hematology, urinalysis) ^k	X	X ^f	X	X	X	X	X ^f	X	X	X	X ^f	X	X	X ^f	X	X	X
Coagulation Profile (PT/INR, D-dimer, fibrinogen) ^k	X	X ^f	X	X	X	X	X ^f	X	X	X	X ^f			X ^f			X
Thyroid Profile Panel ^l	X	X								X		Every 6 weeks					X
IRT Transaction Required	X	X ^m					X				X			X		X	
AE/SAE Assessment	X	X	X	X	X	X	X	X	X	X	X	X	X	X	X	X	X

Table continued on next page

Footnotes

	Scr	Treatment ^a														EOT ^t		
		Cycle 1					Cycle 2					Cycles 3–4 ^b			Cycles 5–6 ^c			
Visit Days	-28 to -1	1	2	4	8	15	1	2	4	8	15	1	8	15	1	8	15	
Window(days)		0	0	0	±1	±1	±1	0	±1	±1	±1	±3	±1	±1	±3	±1	±1	+7
PGx ⁿ		X ⁿ																
Buccal Swab for HLA Typing		X ^f																
Pharmacokinetic: A7517 ^o		X	See Table 6 for detailed sample time points														X	
Pharmacokinetic: Pembrolizumab ^o		X	See Table 6 for detailed sample time points														X	
Anti-WT1 antibody		X ^f					X ^f					X ^f			X ^f			X
Immune Response Biomarker (ELISpot)		X ^f			X	X	X ^f			X	X	X ^f	X	X	X ^f	X	X	X
Immune Response Biomarker (Tetramer)		X ^f				X	X ^f			X	X ^f		X	X ^f		X	X	X
Immune Cell Phenotyping		X ^f			X	X	X ^f			X	X	X ^f	X	X	X ^f	X	X	X
Cytokines		X ^f	X	X	X	X	X ^f	X	X	X	X	X ^f	X	X	X ^f	X	X	X
Circulating Tumor DNA		X ^f					X ^f					X ^f			X ^f			X
Archival Tumor Tissue ^p		X																
Radiographic Disease Assessment ^q	X	Every 56 ± 7 days																
ASP7517 Dosing ^r		X					X					X			X			
Pembrolizumab Dosing ^s		X									X ^s	Every 6 weeks ^s						

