7.1 Efficacy Assessments

Disease response and progression will be evaluated in this study using the RECIST v1.1 and iRECIST criteria as assessed by independent central review and investigator.

Tumor assessments will be performed at screening and at every 8 weeks (\pm 1 week) from C1D1 until confirmed disease progression by iRECIST (iCPD). Scans will be read on site and also submitted in digital format for independent central review. Procedures for independent imaging central review will be described in a separate imaging charter. The assessment will include tumor measurements for target lesions, non-target lesions, and assessment for any new lesions. An overall assessment will be characterized for time point evaluation.

Computed tomography (CT) or magnetic resonance imaging (MRI) scans are preferred for this study and to ensure comparability, the same technique (CT/MRI) used at screening should be utilized throughout the study. The same method should be employed and assessed by the same individual on each occasion, when possible. Imaging should include chest, abdomen and pelvis as well as any other anatomical region appropriate for the participant's disease.

Imaging should be done every 8 weeks from C1D1 regardless of treatment interruption or delays and through the follow-up period as applicable. Scans performed prior to informed consent as standard of care are acceptable as screening scans if done within 28 days prior to C1D1. If a biopsy of a target lesion is performed, the baseline scan should be repeated, if possible.

Confirmatory scans for CR or PR should be done at least 4 weeks after the date of the scan that CR or PR was first observed. Confirmatory scans for PD must occur at least 4 weeks after the date of the scan that PD was first observed but no longer than 8 weeks.

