iUPD before new ACT and is in one of the following cases : a)if the participant stops protocol treatment because they were not judged to be clinically stable, b) no further response assessments are done (because of participant refusal, protocol non-compliance, or participant death); c) the next timepoint responses are all iUPD, and iCPD never occurs;	First date where iUPD criteria are met	Event
Missed ≥ 2 scheduled radiological assessments		
If last assessment prior to missing ≥ 2 scans is iUPD	First date where iUPD criteria are met	Event
If last assessment prior to missing ≥ 2 scans is not iUPD and no progression or death after missing ≥ 2 scans	Date of last radiological assessment	Censor

iPFS		
Situation	Date of Event or Censor	Outcome
No post-baseline tumor imaging prior to missing 2 scans and progression or death after missing ≥ 2 scans	Date of first dose (Day 1)	Censor
No post-baseline tumor imaging prior to missing 2 scans and no progression or death after missing ≥ 2 scans	Date of last radiological assessment	Censor
If radiographical progression or death occurs after missing 2 scheduled radiological assessments and last assessment prior to missing ≥ 2 scans is not iUPD	Date of last radiological assessment before missing 2 scans	Censor

iPFS = Date of Event or Censor – Date of First Dose +1

Missing 2 scheduled imaging assessments:

Missing 2 scheduled imaging assessments is defined as the gap between two imaging assessments being more than 140 days (2.5 times the scheduled imaging assessment interval (2.5 x 56 days)). Imaging assessments after first iUPD will be excluded from PFS derivation.

Note: Participant cannot be censored at “NE”. If NE is the only previous assessment, then iPFS will be censored at Day 1.

To apply the cut-off date to iPFS is to exclude those tumor assessments after cut-off date and anti-cancer therapy date after cut-off date in the analysis.

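### SAP Table 3 (PFS) has no Day 1 row for progression after a gap with no earlier post-baseline scan, so it censors at or before first dose (PFS 0 to −27 days); the start of the first 140-day gap is also not defined

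*SAP*

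**What the plan says.** SAP 5.1.2.5 (iPFS) and 5.1.2.6 (PFS) use the same trigger: "Missing 2 scheduled imaging assessments is defined as the gap between two imaging assessments being more than 140 days", explained as "2.5 times the scheduled imaging assessment interval (2.5 x 56 days". Neither section limits the two assessments to post-baseline scans or says where the first interval begins.

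The two tables then act on the trigger differently.

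- **Table 2 (iPFS)** has a row for "No post-baseline tumor imaging prior to missing 2 scans and progression or death after missing ≥ 2 scans", which censors at the date of first dose. Its last row covers progression or death after two missed scans when the assessment before the gap was not iUPD, and censors at the scan before the gap.
- **Table 3 (PFS)** has one missed-scan row. Any progression or death after the gap is censored at the last scan before it. Table 3 mentions Day 1 only in its first row (no evaluable post-baseline imaging and no death) and in the note on NE.

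The scan calendar is in the protocol. Section 7.1 says "Imaging should be done every 8 weeks from C1D1 regardless of treatment interruption or delays", the schedules of assessments give "Every 56 ± 7 days", and standard-of-care scans taken before consent are "acceptable as screening scans if done within 28 days prior to C1D1".

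**The concern.** A participant who has no scan between screening and a late first post-baseline scan, and who progresses on that scan, has only one earlier image: the screening scan, taken before first dose. Table 3 censors there, and its formula (date minus first dose date plus 1) then returns zero or a negative number. Such a time has no meaning in the planned Kaplan-Meier estimate, so a programmer would have to improvise. Table 2's specific row gives 1 day for the same participant, so PFS and iPFS would be handled differently without a stated reason.

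The undefined start of the first gap adds a second, narrower problem. The 140-day cut suits intervals between post-baseline scans, but the interval from a screening scan can be up to 28 days longer than the interval from first dose. One missed scan might then be counted as two.

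**Working it through.** **Inputs.** Interval 56 days, window ±7 days, scans counted from C1D1 (protocol 7.1 and 1.3). Screening scan b = 1 to 28 days before first dose (protocol 7.1). Rule: gap strictly more than 140 days. PFS time = date − first dose date + 1 (SAP 5.1.2.6). Gaps are differences between dates; w is the deviation of the later scan from schedule, −7 to +7.

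**1. The plan's own figure.** 2.5 × 56 = 140. It reproduces.

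**2. Between post-baseline scans.** One missed: 112 ± 14 = 98 to 126 days. Two missed: 168 ± 14 = 154 to 182 days. The cut of 140 separates them.

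**3. Weeks 8 and 16 both missed, progression at Week 24.** Week 24 falls 168 ± 7 = 161 to 175 days after first dose.

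- Gap from the screening scan: 1 + 161 = 162 to 28 + 175 = 203 days.
- Gap from first dose: 161 to 175 days.

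Both ranges lie wholly above 140, so the rule fires whichever start is used. Table 3 then censors at the screening scan, with PFS time −b + 1:

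| Screening scan | PFS time (Table 3) | iPFS time (Table 2, Day 1 row) |
|---|---|---|
| 1 day before first dose | 0 | 1 |
| 22 days before | −21 | 1 |
| 28 days before | −27 | 1 |

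Table 3's two Day 1 provisions do not help: the Week 24 scan is an evaluable post-baseline scan, and the screening scan is not NE.

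**4. Only Week 8 missed, gap counted from the screening scan.** Gap to Week 16 = b + 112 + w, which runs from 1 + 105 = 106 to 28 + 119 = 147 days. It exceeds 140 only if b + w > 28:

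| b (days before first dose) | Week 16 lateness needed |
|---|---|
| 28 | at least 1 day |
| 25 | at least 4 days |
| 22 | 7 days |
| 21 or fewer | not possible inside the window |

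An on-time Week 16 scan gives at most 28 + 112 = 140, which is not more than 140. Of the 28 × 15 = 420 in-window whole-day combinations, 1 + 2 + 3 + 4 + 5 + 6 + 7 = 28 fire. This counts combinations; it does not estimate how often the case occurs.

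**5. Sensitivity of step 4.** If both end dates are counted (+1), a scan 28 days before first dose with an on-time Week 16 scan gives 141, and 36 of 420 combinations fire. If the nominal-date convention in SAP 6.9.1 also governed scan dates, w = 0 and the gap never exceeds 140. Step 3 still holds with nominal dates: 168 days from first dose, at least 169 from screening.

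**6. First gap counted from first dose.** One miss: 112 ± 7 = 105 to 119 days. Two misses: 161 to 175 days. The cut of 140 separates them with no overlap.

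**The case against.** The strongest reply is that no sentence in the SAP says the first gap starts at the screening scan. Table 2's row for no earlier post-baseline imaging shows that the first interval is covered, but it fits a Day 1 start equally well, and the scan calendar itself runs from C1D1. On that reading a single missed scan never reaches 140 days. This stands: the single-miss case is conditional on one reading of an open definition, and it also needs an early screening scan and a late Week 16 scan together.

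It can also be said that the intended floor is evident, because PFS is defined from the start of treatment and Table 3 uses Day 1 elsewhere. The intention is plausible, but no row writes it down for this case, and step 3 does not depend on where the gap starts.

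Stronger readings that a reader might infer are not supported:

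- **That the 140-day figure is an arithmetic error.** It equals 2.5 × 56 and works between post-baseline scans.
- **That missing Week 8 generally leads to a Week 16 progression being censored.** With gaps taken as date differences, an on-time Week 16 scan never triggers the rule.
- **That 28 of 420 is an incidence of 6.7%.** It would need uniform dates, which no document supports.
- **That an iPFS event is necessarily lost.** A first progression under iRECIST is iUPD. Table 2 makes it an event only if confirmed or in its listed cases a) to c), and it is disregarded if iSD, iPR or iCR follows.
- **That iPFS is cleanly specified where PFS is not.** Table 2's last row also fits a participant whose only earlier scan is screening, and it points to that scan instead of Day 1.

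**Conclusion.** The point holds for Table 3. Applied as written, it gives a PFS time of 0 to −27 days for progression after a gap with no earlier post-baseline scan, and it always does so when Weeks 8 and 16 are missed and progression is seen at Week 24. This assumes that the missed-scan row overrides the ordinary progression row, which is the evident purpose of having it. Table 2 handles the same case at Day 1, subject to its overlapping last row.

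The unnamed start of the first gap is a lesser ambiguity. It misclassifies a single miss only if the gap is counted from a screening scan 22 to 28 days before first dose, actual scan dates are used, and the two offsets sum to more than 28.

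The practical effect is small. PFS and iPFS are secondary, summarized by Kaplan-Meier without a hypothesis test, and the study closed early. Few participants would be affected. SAP version 2.0 nevertheless keeps both endpoints summarized and listed, and with about 12 participants planned per phase 1 arm, one invalid time could be visible in a dose-level curve.

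**What to change.** In SAP 5.1.2.5 and 5.1.2.6:

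1. State that the first gap is measured from the date of first dose.
2. Add Table 2's Day 1 row to Table 3, for progression or death after two missed scans with no earlier post-baseline imaging.
3. State in both tables that the last radiological assessment means a post-baseline one, otherwise Day 1, and that in Table 2 the Day 1 row takes precedence over the last row.

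The cost is one added table row and a few sentences, with no new data. If the database is already locked, the convention used can be documented in the clinical study report.

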5.1.2.4 Overall Survival (OS)

OS is defined as the time from the date of first dose until the date of death from any cause (death date – first dose date + 1). For a participant who is not known to have died by the end of study follow-up, OS is censored at the date of last contact (date of last contact – first dose date + 1).

Table 1 OS Definition

Situation	Date of Event or Censor	Outcome
Death before or on analysis cutoff date	Date of death	Event
Death after analysis cutoff date	Analysis cutoff date	Censor
Last known alive is before or on cutoff date	Last known alive date	Censor
Last known alive is after cutoff date	Analysis cutoff date	Censor

OS = Date of Event or Censor – Date of First Dose +1

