5.1.2.5 Progression-free Survival per iRECIST (iPFS)

iPFS is defined as the time from the start of the study treatment until death from any cause or radiographic disease progression assessed per iRECIST by investigator assessment, whichever occurs first.

If iUPD occurs but iSD, iPR, or iCR is observed any time subsequent to iUPD, iUPD status will be disregarded for determination of iPFS.

Table 2 iPFS Definition

iPFS		
Situation	Date of Event or Censor	Outcome
No evaluable post-baseline imaging assessments, no death	Date of first dose (Day 1)	Censor
Participant did not receive new anti-cancer therapy:		
iCPD	First date where iUPD criteria are met	Event
No iCPD, but death recorded on eCRF	Date of death	Event
No iCPD nor death and not in one of the following cases :a)if the participant stops protocol treatment because they were not judged to be clinically stable, b) no further response assessments are done (because of participant refusal, protocol non-compliance, or participant death); c) the	Date of last radiological assessment	Censor

iPFS		
Situation	Date of Event or Censor	Outcome
next timepoint responses are all iUPD, and iCPD never occurs;		
No iCPD nor death and is in one of the following cases : a)if the participant stops protocol treatment because they were not judged to be clinically stable, b) no further response assessments are done (because of participant refusal, protocol non-compliance, or participant death); c) the next timepoint responses are all iUPD, and iCPD never occurs;	First date where iUPD criteria are met	Event
Participant received new anti-cancer (ACT) therapy:		
No progression before new ACT	Date of last radiological assessment before start of new anti-cancer therapy	Censor
iCPD before new ACT	First date where iUPD criteria are met	Event
iUPD before new ACT and not in one of the following cases : a)if the participant stops protocol treatment because they were not judged to be clinically stable, b) no further response assessments are done (because of participant refusal, protocol non-compliance, or participant death); c) the next timepoint responses are all iUPD, and iCPD never occurs;	Date of last radiological assessment before start of new anti-cancer therapy	Censor

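### The PFS and iPFS cut-off notes leave out deaths, so a death after the cut-off can count as a PFS event later than the same participant's OS censoring date

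*SAP*

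**What the plan says.** OS has an explicit cut-off rule. SAP section 5.1.2.4, Table 1, has separate rows for "Death before or on analysis cutoff date", which is an event at the date of death, and for "Death after analysis cutoff date", which is censored at the cut-off.

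PFS and iPFS have no such rows. Their only cut-off instruction is a sentence under each table. For PFS (section 5.1.2.6) it reads "To apply the cut-off date to PFS is to exclude those tumor assessments after cut-off date and anti-cancer therapy date after cut-off date". For iPFS (section 5.1.2.5) it reads "To apply the cut-off date to iPFS is to exclude those tumor assessments after cut-off date and anti-cancer therapy date after cut-off date".

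The death rows carry no date limit. In Table 3 the situation is "No radiographical progression, but death recorded on eCRF"; in Table 2 it is "No iCPD, but death recorded on eCRF". Both give an event at the date of death. Nothing else in the SAP or protocol was found that removes deaths after the cut-off from PFS or iPFS.

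**The concern.** Each note says what applying the cut-off consists of, and the list has two items. Followed as written, a death after the cut-off stays in the data and meets an event row, while OS censors that same death. A participant can then have a PFS time longer than the OS time, which cannot be right when both run from first dose.

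Follow-up would also be used selectively. Participants who die after the cut-off contribute extra time and an event; those still alive are censored at their last scan before it. The PFS event count would then depend on how long after the cut-off the data were extracted. Excluding later therapy dates adds to this, because it disables the Table 3 row that would have censored a death following new therapy.

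**Working it through.** **Inputs.** The two times share an origin and compare directly: "OS = Date of Event or Censor – Date of First Dose +1" and "PFS = Date of Event or Censor – Date of First Dose +1". Day 1 is the first dose, so an event or censoring on Day n gives a time of n days. The only other rule that could catch a late death is the missed-scan rule. Its threshold reproduces as stated: 2.5 × 56 = 140 days.

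**Method.** Tables 1 and 3 were applied as written to hypothetical participants, then again with deaths after the cut-off also excluded. Table 2 was read, not run; its death row and note have the same form. Unless stated otherwise, scans without progression fall on Days 57, 113, 169, 225 and 281, and the assumed cut-off is Day 300. E = event, C = censored.

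| Case | OS | PFS as written | PFS with deaths excluded |
|---|---|---|---|
| A. Death Day 340 | C 300 | E 340 | C 281 |
| B. As A, progression on a Day 330 scan | C 300 | E 340 | C 281 |
| C. As A, new therapy Day 320 | C 300 | E 340 | C 281 |
| D. As A, new therapy Day 290 | C 300 | C 281 | C 281 |
| E. Progression Day 225, death Day 340 | C 300 | E 225 | E 225 |
| F. Death Day 430 | C 300 | C 281 or E 430 | C 281 |
| G. No post-baseline scan, cut-off Day 40, death Day 70 | C 40 | E 70 | C 1 |

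**Reading the cases.**

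- A: the PFS event falls 340 − 300 = 40 days after the OS censoring date. The gap from last scan to death is 340 − 281 = 59 days, under 140, so the missed-scan rule does not apply.
- B: the progression seen on Day 330 is dropped but the death is kept, so PFS runs 10 days past an observed progression.
- C: with the Day 320 therapy date retained, Table 3 would censor at Day 281. Dropping it turns a censored participant into an event.
- D and E: progression or new therapy on or before the cut-off settles the outcome, and there is no anomaly.
- F: the gap from last scan to death is 430 − 281 = 149 days, over 140. The SAP defines the gap as one between two imaging assessments. If it is instead measured to death, PFS is censored at Day 281; on the literal wording, it is an event at Day 430. The overshoot past the cut-off is therefore at most 140 days on the first reading and unbounded on the second.
- G: with no post-baseline scan, the first row of Table 3 gives Day 1 once the death is excluded.

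DOR and iDOR carry the same cut-off sentence, but death is not an event in either definition, so they are not affected in this way.

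**The case against.** The strongest objection is that this may never occur in this study. SAP section 6.8 plans no interim analysis, section 5.1.1 records early closure, and no cut-off or extraction date is given. If the one final analysis takes all data to last follow-up, no death falls after the cut-off. That stands as a limit on reach. It does not rescue the text, because Table 1 expressly provides for deaths after the cut-off.

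A second objection is that Table 1 already settles how the cut-off treats deaths, and the PFS notes merely add two further data types. A programmer who reused the OS death variable would never meet the problem. That is a reasonable inference about intent, but the SAP does not say it. Table 1 sits within the OS definition, and two programmers following the text could differ.

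Third, PFS and iPFS are secondary, single-arm Kaplan-Meier summaries. No hypothesis, iORR result or decision rule depends on them. That also stands.

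A reader might infer a stronger point: that this trial's PFS estimates are biased, by an amount that can be gauged from the survival figures in protocol section 2.2. The documents do not support it. Those figures run from about 5 months (stage 4 colorectal cancer without chemotherapy), through less than 15 months (recurrent ovarian cancer), to at least 2 years (advanced melanoma). Any calculation from them gives the share of everyone alive at the cut-off who then die, whereas only participants still without progression or new therapy are affected. Accrual, actual cohort sizes and the lag from cut-off to extraction are not given.

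**Conclusion.** Wrong as written, minor. The stated rule gives PFS and iPFS events after the cut-off, and later than the same participant's OS censoring date, under four conditions: the database holds deaths after the cut-off; the participant has no qualifying progression by then; no new anti-cancer therapy has started by then; and the missed-scan rule does not catch the death.

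The 40-day excess in case A rests on assumed dates and illustrates the rule; it does not estimate an effect in this trial. The number affected cannot be computed from the documents and may be zero. Any effect would fall on event counts and the tails of secondary descriptive curves. The primary response rate, sample size and type I error are untouched.

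**What to change.** In the notes under Tables 2 and 3, add deaths to the exclusions, for example: *drop tumor assessments, new anti-cancer therapy starts and deaths dated after the cut-off*. Then let the existing rows set the outcome: last assessment, last assessment before new therapy or before the missed scans, or Day 1 where there is no evaluable post-baseline scan. For iPFS, the rows on unconfirmed progression apply as they stand.

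Do not add a separate clause censoring all such participants at the last scan before the cut-off, because it would override those rows. Take new therapy on Day 120, scans without progression on Days 57, 113 and 169, cut-off on Day 200 and death on Day 230. Table 3 censors at Day 113, the last scan before the new therapy; a blanket clause would give Day 169. It would also displace the missed-scan date and leave a participant with no post-baseline scan without a date.

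The cost is a few words in two SAP notes and one condition in the derivation programs, with no new data.
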